3.3 REGISTRY DURATION/FOLLOW-UP

All subjects enrolled in this registry will be evaluated preoperatively and followed from their treatment date through 24-months postprocedure. Subjects will have a baseline standard clinical evaluation and standard follow-up evaluations, including carotid duplex imaging, at 1 to 3-months, 6-months, 12-months, and 24-months postprocedure. If intraoperative completion duplex or other imaging (i.e., CTA, MRA, arteriography) is performed, data should be collected, but this is not mandatory.

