5.8 REGISTRY EXIT

Subjects will be exited from the registry following their scheduled 24-month follow-up evaluation, or earlier if the subject withdraws from the registry, or his/her participation is discontinued by the Investigator, or death. The date each subject completed the registry per this protocol, or if not, then the date the subject exited from the registry and the primary reason should be recorded. Any subject who experiences a serious carotid and/or device related adverse event that is ongoing at the time of exit will be followed by the physician until the adverse event is resolved or the subject is medically stable in the opinion of the Investigator.

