6.0 REPORTING OF ADVERSE EVENTS AND SERIOUS ADVERSE EVENTS

6.1 DEFINITIONS

An “Adverse Event” (AE) is any clinical finding that is an undesired or pathological change in a registry subject as indicated by signs, symptoms, illnesses and events that develop or worsen in severity in association with the registry whether or not thought to be related to the device or procedure. Adverse events include current illness, injuries, side effects, toxicities, allergic reactions, or events that occur or worsen during the course of a clinical study. This registry will only collect carotid procedure and device related adverse events as well as any carotid related clinical findings.

Adverse Events will be classified as Serious Adverse Events (SAEs) if the event:

- is life threatening (even if temporary in nature) or fatal;
- results in permanent impairment of a body function or permanent damage to a body structure;
- requires medical or surgical intervention to preclude permanent impairment of a body function or permanent damage to a body structure; or
- requires or prolongs hospitalization.

Once a clinical finding is noted, and the finding is classified as an AE or SAE, the relationship to the device will be classified as follows:

- Not Related: The event is due to an underlying or concurrent illness or effect of another device, drug or intervention and is not related to the use of the registry device.

- **Possible:** The event has a strong temporal relationship to the use of the registry device, and an alternative etiology is equally or less likely.
- **Probable:** The event has a strong temporal relationship to the use of the registry device, and another etiology is unlikely or significantly less likely.
- **Definite:** An event that can only be attributed to the use of the registry device.

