11.2 DATA ANALYSIS

For continuous variables such as subject age, the mean, standard deviation, median and range will be presented. For categorical variables such as presence of conditions observed under medical history, the number experiencing the condition over the total number completing the registry, the percentage, and the exact 95% confidence interval on the percentage will be presented.

Carotid procedure and device related serious adverse events will be listed and the time course, outcome, severity and possible relationship to the device will be documented.

Time to event analysis, when deemed necessary, will be performed using Kaplan Meier methods with any comparisons done via log-rank testing.

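### Section 11.2 names only Kaplan-Meier and gives no rule for death; if deaths are censored, an optional time-to-event rate for a non-fatal outcome would modestly overstate the proportion of subjects affected

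*Combined protocol and SAP*

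**What the plan says.** Section 11.2 has one sentence on time-to-event analysis: "Time to event analysis, when deemed necessary, will be performed using Kaplan Meier methods", with log-rank tests for any comparisons. It is conditional. It names no event, time origin or censoring rule, and no competing-risk method appears anywhere in the document. The summary that 11.2 does commit to for categorical variables is "the number experiencing the condition over the total number completing the registry, the percentage, and the exact 95% confidence interval on the percentage".

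Death appears in 5.8 as a reason for leaving the registry: subjects exit after the 24-month visit "or earlier if the subject withdraws from the registry, or his/her participation is discontinued by the Investigator, or death". For those who do not complete, "the date the subject exited from the registry and the primary reason should be recorded". Section 6.1 limits what counts as a collected event: "This registry will only collect carotid procedure and device related adverse events as well as any carotid related clinical findings". Under 3.3, subjects are "followed from their treatment date through 24-months postprocedure", with duplex imaging at 1 to 3, 6, 12 and 24 months. Recurrent stenosis, stroke and infection are in the risk list in 7.1. None of them is defined as an endpoint with a 24-month rate.

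**The concern.** A subject who dies cannot later develop recurrent stenosis or a patch infection. Read together, the three sections lead to censoring by default. An unrelated death is not an outcome event (6.1), it is recorded as an exit (5.8), and the only named method handles a subject who exits without the event by censoring (11.2). One minus Kaplan-Meier then describes a population in which nobody dies.

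The registry's aim in 2.0 is to document clinical outcomes, and 8.3.4 foresees publication and regulatory submissions. A reader of a 24-month figure would take it as the proportion of treated subjects who had the event. The gap between the two quantities does not shrink with more subjects, and a confidence interval does not reveal it.

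**Working it through.** The plan states no event rate, mortality or precision target, so there is no figure of its own to reproduce. From the documents come the 24-month follow-up (3.3), the visit times (3.3) and the cap of 230 subjects (3.2). The 24-month one-minus-Kaplan-Meier risk q and the 24-month mortality m are assumptions, shown as ranges.

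**Main comparison.** Take constant, independent hazards over 24 months: h = −ln(1 − q) for the event and d = −ln(1 − m) for death.

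- With deaths censored, one minus Kaplan-Meier estimates 1 − exp(−h) = q.
- The cumulative incidence with death competing is h/(h + d) × [1 − exp(−(h + d))].

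For q = 10% and m = 20%, h = 0.1054 and d = 0.2231. The cumulative incidence is 0.1054/0.3285 × (1 − 0.90 × 0.80) = 0.3207 × 0.28 = 8.98%.

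| q (1 − KM) | m | Cumulative incidence | Excess (points) | Ratio |
|---|---|---|---|---|
| 10% | 5% | 9.75% | 0.25 | 1.025 |
| 10% | 10% | 9.50% | 0.50 | 1.053 |
| 10% | 15% | 9.24% | 0.76 | 1.082 |
| 10% | 20% | 8.98% | 1.02 | 1.114 |
| 20% | 20% | 18.0% | 2.0 | 1.111 |

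**Early events.** With q = 5% and m = 10%, constant hazards give 4.75%, an excess of 0.25 points. If the whole event hazard falls in month 1, the cumulative incidence is 4.99%, an excess of 0.01 points.

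**Scale.** The approximate 95% half-width with all 230 subjects is 1.96 × √(q(1 − q)/230): 3.9 points at q = 10% and 5.2 points at q = 20%.

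**Limit for restenosis.** Suppose restenosis is seen only at scans, at months 2 (for the 1 to 3-month visit), 6, 12 and 24, and only in subjects alive at the scan. The detectable incidence is then the sum over intervals (a, b) of exp(−d·b/24) × [exp(−h·a/24) − exp(−h·b/24)].

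| q | m | Cumulative incidence | Detectable at scans | Shortfall (points) |
|---|---|---|---|---|
| 10% | 5% | 9.75% | 9.67% | 0.08 |
| 10% | 10% | 9.50% | 9.33% | 0.17 |
| 10% | 20% | 8.98% | 8.65% | 0.33 |
| 20% | 20% | 18.0% | 17.34% | 0.66 |

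Under these assumptions, a cumulative incidence built on scan-detected restenosis runs low by about a third of the amount by which one minus Kaplan-Meier runs high (0.17 against 0.50; 0.66 against 2.0).

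**The case against.** A reader might infer that the plan will report a 24-month restenosis rate that is overstated. The documents do not support that. Time-to-event analysis is optional, no event is named for it, and recurrent stenosis appears only as a risk. The affected figure may never be produced.

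A reader might also infer that the plan instructs deaths to be censored. It does not; it is silent. Kaplan-Meier could be applied to all-cause death or to a composite that includes death, where it is appropriate. Censoring is the default consequence for a non-fatal outcome, not a stated rule.

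Nor is one minus Kaplan-Meier always too high once deaths occur. If the deaths come after the last event, the two estimates coincide. If the target is the risk in the absence of death, Kaplan-Meier estimates it without bias under independent censoring. The plan names no target.

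The size is also small. In every case tabulated the excess is below the sampling half-width at 230 subjects, and no performance goal or comparator exists that it could tip. The completer denominator in the same section can distort more. At q = 10% and m = 10%, with no other loss and all events kept in the numerator, events over completers is 9.50/0.90 = 10.6%, against a cumulative incidence of 9.5% and a one-minus-Kaplan-Meier of 10.0%.

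All of this stands, and it limits the weight of the point. It does not remove it. If the optional analysis is run on a non-fatal outcome, the named method answers a different question from the one readers will assume, and the plan does not say so.

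**Conclusion.** The point holds conditionally and is minor. If a non-fatal outcome is analysed by Kaplan-Meier with deaths censored, and the result is read as the proportion of treated subjects who have the event, it will be at or above the cumulative incidence. The likely excess is about 0.25 to 1.0 points at a 10% one-minus-Kaplan-Meier with 5% to 20% mortality, 2.0 points at 20% and 20%, and near zero for events concentrated early. These figures rest on assumed rates and on constant, independent hazards. The point matters most for later outcomes such as recurrent stenosis. The completer denominator is a separate problem that this change does not address.

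**What to change.** Add to 11.2 wording along these lines:

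> Any time-to-event estimate for a non-fatal outcome (such as recurrent stenosis, stroke or infection) will be the Aalen-Johansen cumulative incidence, with death without the event as a competing event. Dates and reasons of exit will be those recorded under 5.8. Kaplan-Meier will be used for all-cause death and for composites that include death.

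Confirm that the exit date recorded for a death is the date of death. If the sponsor wants the risk in the absence of death, 11.2 should say so and state the independence assumption.

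State one limit alongside any restenosis estimate: restenosis is seen mainly at scheduled duplex visits, so restenosis that precedes a death between scans can be missed. The 12 to 24-month interval is the longest.

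The cost is a sentence or two and standard software, with no new data.

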11.3 FINAL REPORT

A final report will be prepared by the Sponsor at the conclusion of this registry which will summarize all of the data collected, the parameters of all treatments and all carotid procedure and device related serious adverse events recorded during the registry. Copies of the final report will be provided to the Investigator and IRB.
